⁵ FDA Liver Guidance Document 2009 Guidance for Industry: Drug Induced Liver Injury – Premarketing Clinical Evaluation

Version Number: 1.8

Date: July 26, 2019		 If it worsens, depending on the severity, treat as Grade 2 or Grade 3 or 4. Consider symptomatic treatment including hydration, electrolyte replacement, diuretics, etc.
Grade 2 [serum creatinine > 1.5- × baseline; > 1.5 3.0 × ULN]		 For Grade 2 elevated creatinine: Consider symptomatic treatment including hydration, electrolyte replacement, diuretics, etc. Carefully monitor serum creatinine every 2-3 days and as clinically warranted. Consult nephrologist and consider renal biopsy if clinically indicated. If event is persistent (> 3-5 days) or worsens, promptly start prednisone 1 to 2 mg/kg/day or IV equivalent. If event is not responsive within 3-5 days or worsens despite prednisone at 1-2 mg/kg/day or IV equivalent, additional work-up should be considered and prompt treatment with IV methylprednisolone at 2-4 mg/kg/day started. Once improving gradually taper steroids over ≥ 28 days and consider prophylactic antibiotics, antifungals and anti PCP treatment (please refer to current NCCN guidelines for treatment of cancer-related infections [Category 2B recommendation]). When event returns to baseline, resume study drug/study regimen and routine serum creatinine monitoring per study protocol.
Grade 3 or 4 (Grade 3: serum creatinine > 3.0 shaseline; > 3.0-6 ULN Grade 4: serum creatinine > 6.0 ULN)	× 0.	 Carefully monitor serum creatinine on daily basis. Consult Nephrologist and consider renal biopsy if clinically indicated. Promptly start prednisone 1 to 2 mg/kg/day or IV equivalent. If event is not responsive within 3-5 days or worsens despite prednisone at 1-2 mg/kg/day or IV equivalent, additional work-up should be considered and prompt treatment with IV methylprednisolone 2-4 mg/kg/day started. Once improving, gradually taper steroids over ≥ 28 days and consider prophylactic antibiotics, antifungals and anti PCP treatment (please refer to current NCCN guidelines for treatment of cancer-related infections [Category 2B recommendation]).

Version Number: 1.8 Date: July 26, 2019

Date: July 26, 2019		1 7	
Rash (excluding bullous skin formations)	Grade of skin rash (please refer to NCI CTCAE v4.03 for definition of severity/grade depending on type of skin rash)	Any grade	Monitor for signs and symptoms of dermatitis (rash and pruritus) **IF THERE IS ANY BULLOUS FORMATION, THE STUDY PHYSICIAN SHOULD BE CONTACTED AND STUDY DRUG DISCONTINUED**
	Grade 1	No dose modification	 For Grade 1: Consider symptomatic treatment including oral antipruritics (e.g., diphenhydramine or hydroxyzine) and topical therapy (e.g., urea cream).
	Grade 2	For persistent (> 1- 2 weeks) Grade 2 events, hold scheduled study drug/study regimen until resolution to ≤ Grade 1 or baseline. • If toxicity worsens then treat as Grade 3 • If toxicity improves then resume administration at next scheduled dose Study drug/study regimen can be resumed at the next scheduled dose once event stabilizes to Grade ≤ 1 or baseline and 5-7 days have passed after completion of steroid taper.	 For Grade 2: Obtain dermatology consult. Consider symptomatic treatment including oral antipruritics (e.g., diphenhydramine or hydroxyzine) and topical therapy (e.g., urea cream). Consider moderate strength topical steroid. If no improvement of rash/skin lesions occurs within 3-5 days or is worsening despite symptomatic treatment and/or use of moderate strength topical steroid, discuss with Study Physician and promptly start systemic steroids prednisone 1-2 mg/kg/day or IV equivalent. Consider skin biopsy if persistent for > 1-2 weeks or recurs.
	Grade 3	 Hold study drug/study regimen until resolution to ≤ Grade 1 or baseline Resume study drug/study regimen administration at the next scheduled dose if elevations downgrade ≤ Grade 1 or baseline 	 For Grade 3 or 4: Consult dermatology. Promptly initiate empiric IV methylprednisolone 1 to 4 mg/kg/day or equivalent. Consider hospitalization. Monitor extent of rash [Rule of Nines]. Consider skin biopsy (preferably more than 1) as clinically feasible. Once improving, gradually taper steroids over ≥ 28 days and consider prophylactic antibiotics, antifungals and anti PCP treatment (please refer to current NCCN guidelines for treatment of cancer-related infections [Category 2B recommendation]). Discuss with Study Physician.
	Grade 4	Permanently discontinue study drug/study	

Version Number: 1.8 Date: July 26, 2019

		regimen.	
(e.g., hyperthyroidism, hypothyroidism, hypopituitarism, adrenal insufficiency,	Any grade (depending on the type of endocrinopathy, refer to NCI CTCAE v4.03 for defining the CTC grade/severity)		 Consult Endocrinologist. Monitor subjects for signs and symptoms of endocrinopathies. Non-specific symptoms include headache, fatigue, behavior changes, changed mental status, vertigo, abdominal pain, unusual bowel habits, hypotension and weakness. Subjects should be thoroughly evaluated to rule out any alternative etiology (e.g., disease progression including brain metastases, infections, etc). Monitor and evaluate thyroid function tests: thyroid stimulating hormone (TSH), free triiodothyronine and free thyroxine (T₄) and other relevant endocrine labs depending on suspected endocrinopathy. If a subject experiences an AE that is thought to be possibly of autoimmune nature (e.g., thyroiditis, pancreatitis, hypophysitis, diabetes insipidus), the investigator should send a blood sample for appropriate autoimmune antibody testing.
	Grade 1 (depending on the type of endocrinopathy, refer to NCI CTCAE v4.03 for defining the CTC Grade 1)	No dose modification	For Grade 1: (including those with asymptomatic TSH elevation) Monitor subject with appropriate endocrine function tests If TSH < 0.5 × lower limit of normal, or TSH > 2 × ULN or consistently out of range in 2 subsequent measurements, include free T ₄ at subsequent cycles as clinically indicated and consider endocrinology consult.
	Grade 2 (depending on the type of endocrinopathy, refer to NCI CTCAE v4.03 for defining the CTC grade/severity 2)	 For Grade 2 endocrinopathy other than hypothyroidism, hold study drug/study regimen dose until subject is clinically stable. If toxicity worsens then treat as Grade 3 or Grade 4 If toxicity improves to baseline then treat at next scheduled treatment date Study drug/study regimen can be resumed at the next scheduled dose once event stabilizes to Grade ≤ 1 and 5-7 days have passed after completion of steroid taper 	 For Grade 2: (including those with symptomatic endocrinopathy) Isolated hypothyroidism may be treated with replacement therapy without treatment interruption and without corticosteroids. Initiate hormone replacement as needed for management. Evaluate endocrine function, and as clinically indicated, consider pituitary scan. For subjects with abnormal endocrine work-up, except for those with isolated hypothyroidism, consider short-term, corticosteroids (e.g., 1-2 mg/kg/day methylprednisolone or IV equivalent) and prompt initiation of treatment with relevant hormone replacement (e.g., levothyroxine, hydrocortisone, or sex hormones).

Version Number: 1.8

Grade 3 or 4 (depending on the type of endocrinopathy, refer to NCI CTCAE v4.03 for defining the CTC grade/severity 3 or 4)	 Subjects with endocrinopathies who may require prolonged or continued steroid replacement can be retreated with study drug/study regimen on the following conditions: 1) the event stabilizes and is controlled, 2) the subject is clinically stable as per Investigator or treating physician's clinical judgment, and 3) doses of prednisone are at less than or equal to 10mg/day or equivalent. For Grade 3 or 4 endocrinopathy other than hypothyroidism, hold study drug/study regimen dose until endocrinopathy symptom(s) are controlled Resume study drug/study regimen administration if controlled at the next scheduled dose Study drug/study treatment can be resumed based upon treating physician's clinical judgment at the next scheduled dose once event stabilizes to Grade ≤ 1 or baseline and 5-7 days have passed after completion of steroid taper For drade 3 or 4: For Grade 3 or 4:
Grade of neurotoxicity Depending on the type of neurotoxicity, refer to NCI CTCAE v4.03 for defining the CTC grade/ severity Any grade	Subjects should be evaluated to rule out any alternative etiology
	Grade of neurotoxicity Depending on the type of endocrinopathy, refer to NCI CTCAE v4.03 for defining the CTC grade/severity 3 or 4) Grade of neurotoxicity Depending on the type of neurotoxicity, refer to NCI CTCAE v4.03 for defining the CTC grade/severity

Date: July 26, 2019	T	'	
gravis and Guillain-Barré)	Grade 1 Grade 2	No dose modifications • For acute motor neuropathies or neurotoxicity, hold study drug/study regimen dose until resolution to ≤ Grade 1 • For sensory neuropathy/neuropathic pain, consider holding study drug/study regimen dose until resolution to ≤ Grade 1. - If toxicity worsens then treat as Grade 3 or Grade 4 - If toxicity improves to baseline then treat at next scheduled treatment date • Study drug/study regimen can be resumed at the next scheduled dose once event stabilizes to Grade ≤ 1 and 5-7 days have passed after completion of steroid taper	 (e.g., disease progression, infections, metabolic syndromes and medications, etc). Monitor subject for general symptoms (headache, nausea, vertigo, behavior change, or weakness). Consider appropriate diagnostic testing (e.g., electromyogram and nerve conduction investigations). Symptomatic treatment with neurological consult as appropriate. See "Any Grade" recommendations above. Discuss with the Study Physician. Obtain Neurology Consult. Sensory neuropathy/neuropathic pain may be managed by appropriate medications (e.g., gabapentin, duloxetine, etc). Promptly start systemic steroids prednisone 1-2 mg/kg/day or IV equivalent. If no improvement within 3-5 days despite 1-2 mg/kg/day prednisone or IV equivalent consider additional work-up and promptly treat with additional immunosuppressive therapy (e.g., IVIG).
	Grade 3	 Hold study drug/study regimen dose until resolution to ≤ Grade 1 Resume study drug/study regimen administration at the next scheduled dose if elevations downgrade ≤ Grade 1 or baseline 	 For Grade 3 or 4: Discuss with Study Physician. Obtain Neurology Consult. Consider hospitalization. Promptly initiate empiric IV methylprednisolone 1 to 2 mg/kg/day or equivalent.
	Grade 4	Permanently discontinue study drug/study regimen	 If no improvement within 3-5 days despite IV corticosteroids, consider additional work-up and promptly treat with additional immunosuppressants (e.g., IVIG). Once stable, gradually taper steroids over ≥ 4 weeks.
 			The prompt diagnosis of immune-mediated peripheral

Date: July 26, 2019		'	
mediated peripheral neuromotor syndromes, such as Guillain-Barré and myasthenia gravis			neuromotor syndromes is important, since certain subjects may unpredictably experience acute decompensations which can result in substantial morbidity or in the worst case, death. Special care should be taken for certain sentinel symptoms which may predict a more severe outcome, such as prominent dysphagia, rapidly progressive weakness, and signs of respiratory insufficiency or autonomic instability. • Subjects should be evaluated to rule out any alternative etiology (e.g., disease progression, infections, metabolic syndromes and medications, etc). It should be noted that the diagnosis of immune-mediated peripheral neuromotor syndromes can be particularly challenging in subjects with underlying cancer, due to the multiple potential confounding effects of cancer (and its treatments) throughout the neuraxis. Given the importance of prompt and accurate diagnosis, it is essential to have a low threshold to obtain a neurological consult. • Neurophysiologic diagnostic testing (e.g., electromyogram and nerve conduction investigations, and "repetitive stimulation" if myasthenia is suspected) are routinely indicated upon suspicion of such conditions and may be best facilitated by means of a neurology consultation. • Important to consider that the use of steroids as the primary treatment of Guillain-Barré is not typically considered effective. Subjects requiring treatment should be started with IVIG and followed by plasmapheresis if not responsive to IVIG.
	Grade 1	No dose modification	 Discuss with the Study Physician. Care should be taken to monitor subjects for sentinel symptoms of a potential decompensation as described above. Obtain a neurology consult unless the symptoms are very minor and stable.
	Grade 2	 Hold study drug/study regimen dose until resolution to ≤ Grade 1 Resume study drug/study regimen administration at the next scheduled dose if elevations downgrade ≤ Grade 1 or baseline 	 Grade 2: Discuss with the Study Physician. Care should be taken to monitor subjects for sentinel symptoms of a potential decompensation as described above. Obtain a Neurology Consult. Sensory neuropathy/neuropathic pain may be managed

Date: July 26, 2019	1		
Date: July 26, 2019			by appropriate medications (e.g., gabapentin, duloxetine, etc). MYASTHENIA GRAVIS Steroids may be successfully used to treat Myasthenia Gravis. Important to consider that steroid therapy (especially with high doses) may result in transient worsening of myasthenia and should typically be administered in a monitored setting under supervision of a consulting neurologist. Subjects unable to tolerate steroids may be candidates for treatment with plasmapheresis or IVIG. Such decisions are best made in consultation with a neurologist, taking into account the unique needs of each subject. If Myasthenia Gravis-like neurotoxicity present, consider starting acetylcholinesterase (AChE) inhibitor therapy in addition to steroids. Such therapy, if successful, can also serve to reinforce the diagnosis. GUILLAIN-BARRÉ: Important to consider here that the use of steroids as the primary treatment of Guillain-Barré is not typically considered effective. Subjects requiring
	Grade 3	 Hold study drug/study regimen dose until resolution to ≤ Grade 1 Resume study drug/study regimen administration at the next scheduled dose if elevations downgrade ≤ Grade 1 or baseline Permanently discontinue study drug/study regimen. 	treatment should be started with IVIG and followed by plasmapheresis if not responsive to IVIG. • For severe or life threatening (Grade 3 or 4) events: - Discuss with Study Physician. - Recommend hospitalization. - Monitor symptoms and obtain neurological consult. • MYASTHENIA GRAVIS • Steroids may be successfully used to treat Myasthenia Gravis. It should typically be administered in a monitored setting under supervision of a consulting neurologist. • Subjects unable to tolerate steroids may be candidates for treatment with plasmapheresis or IVIG.

Drug Substances: Durvalumab, MEDI0457 Study Numbers: 2017-0302, ESR-16-12202 Version Number: 1.8

Version Number: 1.8 Date: July 26, 2019	Proprietary of MD Anderson Cancer Center
	○ If Myasthenia Gravis-like neurotoxicity present, consider starting AChE inhibitor therapy in addition to steroids. Such therapy, if successful, can also serve to reinforce the diagnosis. ○ GUILLAIN-BARRÉ: ○ Important to consider here that the use of steroids as the primary treatment of Guillain-Barré is not typically considered effective. Subjects requiring treatment should be started with IVIG and followed by plasmapheresis if not responsive to IVIG.

Version Number: 1.8 Date: July 26, 2019

Table 8. Treatment Modification and Toxicity Management Guidelines for Infusion-related Reactions (Durvalumab)

Severity Grade	Dose Modifications	Toxicity Management
Any grade		 Management per institutional standard at the discretion of investigator. Monitor subjects for signs and symptoms of infusion-related reactions (e.g., fever and/or shaking chills, flushing and/or itching, alterations in heart rate and blood pressure, dyspnea or chest discomfort, skin rashes etc) and anaphylaxis (e.g., generalized urticaria, angioedema, wheezing, hypotension, tachycardia, etc).
Grade 1	The infusion rate of study drug/study regimen may be decreased by 50% or temporarily interrupted until resolution of the event.	 For Grade 1 or Grade 2: Acetaminophen and/or antihistamines may be administered per institutional standard at the discretion of the investigator.
Grade 2	The infusion rate of study drug/study regimen may be decreased 50% or temporarily interrupted until resolution of the event. Subsequent infusions may be given at 50% of the initial infusion rate.	Consider premedication per institutional standard prior to subsequent doses.
Grade 3/4	Permanently discontinue study drug/study regimen.	For Grade 3 or 4: Manage severe infusion-related reactions per institutional standards (e.g., intramuscular epinephrine, followed by intravenous diphenhydramine and ranitidine, and intravenous glucocorticoid).

Version Number: 1.8 Date: July 26, 2019

Table 9. Treatment Modification and Toxicity Management Guidelines for Non-immune-mediated Reactions (Durvalumab)

CTC Grade/Severity	Dose Modification	Toxicity Management
Any grade	Note: dose modifications are not required for adverse events (AEs) not deemed to be related to study treatment (i.e., events due to underlying disease) or for laboratory abnormalities not deemed to be clinically significant.	Treat accordingly as per institutional standard.
1	No dose adjustment.	Treat accordingly as per institutional standard.
2	Hold study drug/study regimen until resolution to ≤ Grade 1 or baseline.	Treat accordingly as per institutional standard.
3	Hold study drug/study regimen until resolution to ≤ Grade 1 or baseline For AEs that downgrade to ≤ Grade 2 within 7 days or resolve to ≤ Grade 1 or baseline, resume study drug/study regimen administration at next scheduled dose based upon treating physician's clinical judgment. Otherwise, discontinue study drug/study regimen.	Treat accordingly as per institutional standard.
4	Discontinue study drug/study regimen (Note for Grade 4 labs, decision to discontinue would be based on accompanying clinical signs/symptoms and as per Investigator's clinical judgment and in consultation with the MDACC IND Office and supporting companies).	Treat accordingly as per institutional standard.

Version Number: 1.8
Date: July 26, 2019

Proprietary of MD Anderson Cancer Center

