6.7. Management of IP-related Toxicities

6.7.1. **Dose Management**

Either treatment may be stopped by the investigator while the other treatment continues. MEDI0457 doses should not be modified.

For AEs that are considered at least partly due to administration of durvalumab the following dose adjustment guidance may be applied:

- Treat each of the toxicities with maximum supportive care (including holding durvalumab).
- If the symptoms promptly resolve with supportive care, consideration should be given to continuing the same dose of durvalumab along with appropriate continuing supportive care. If medically appropriate, dose modifications are permitted for durvalumab.
- All dose modifications should be documented with clear medical reasoning and documentation of the approach taken.

In addition, there are certain circumstances in which durvalumab should be permanently discontinued (Appendix D, Postow 2015).

Following the first dose of durvalumab, subsequent administration of durvalumab can be modified based on toxicities observed (Appendix D, Postow 2015). All toxicities will be graded according to NCI CTCAE version 4.03.

Based on the mechanism of action of durvalumab leading to T-cell activation and proliferation, there is the possibility of observing irAEs during the conduct of this study. Potential irAEs include immune-mediated dermatitis, hepatitis/hepatotoxicity, endocrinopathy (hypothyroidism, hyperthyroidism, hypophysitis, and adrenal insufficiency), neuropathy/neuromuscular toxicity, nephritis, pancreatitis (elevated lipase/amylase), pneumonitis, and colitis. Patients should be monitored for signs and symptoms of irAEs. In the absence of an alternate etiology (e.g., infection or PD) signs or symptoms of dermatitis, hepatitis/hepatotoxicity, endocrinopathy

Version Number: 1.8

Proprietary of MD Anderson Cancer Center Date: July 26, 2019

(hypothyroidism, hyperthyroidism, hypophysitis, and adrenal insufficiency), neuropathy/neuromuscular toxicity, nephritis, pancreatitis (elevated lipase/amylase), pneumonitis, and colitis should be considered to be immune-related.

Dose modifications will not be required for AEs that are clearly not attributable to durvalumab (such as an accident) or for laboratory abnormalities that are not deemed to be clinically significant. Administration may continue despite concurrent vitiligo of any AE grade.

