Acetaminophen and/or an antihistamine (e.g., diphenhydramine) or equivalent medications per institutional standard may be administered prior to infusion at the discretion of the investigator for primary prophylaxis against infusion-related reactions. In the event of Grade ≤ 2 infusion-related reaction, the infusion rate of durvalumab may be decreased by 50% or interrupted until resolution of the event (up to 4 hours) and re-initiated at 50% of the initial rate until completion of the infusion. In patients experiencing Grade ≤ 2 infusion-related reaction, subsequent infusions may be administered at 50% of the initial rate. If a patient experiences an infusion-related reaction, acetaminophen and/or an antihistamine (e.g., diphenhydramine) and/or corticosteroid or equivalent medications per institutional standard may be administered prior to subsequent infusions at the discretion of the investigator for secondary prophylaxis of infusionrelated reactions. If the infusion-related reaction is Grade 3 or higher in severity, treatment with durvalumab will be discontinued.

As with any antibody, allergic reactions to dose administration are possible. Appropriate drugs and medical equipment to treat acute anaphylactic reactions must be immediately available, and study personnel must be trained to recognize and treat anaphylaxis. The study site must have immediate access to emergency resuscitation teams and equipment in addition to the ability to admit patients to an intensive care unit if necessary.

6.7.2. **Dose-limiting Toxicities**

Grading of DLTs will be according to the NCI CTCAE version 4.03.

A DLT will be defined as any Grade 3 or higher treatment-related toxicity that occurs during the DLT evaluation period (i.e., 4 weeks after the first dose of durvalumab is administered for the initial six patients), including the following treatment-related toxicities:

- a. Any Grade 4 irAE is a DLT.
- b. Any \geq Grade 3 colitis is a DLT.
- c. Any \geq Grade 3 non-infectious pneumonitis irrespective of duration is a DLT.
- d. Any Grade 2 pneumonitis that does not resolve to \leq Grade 1 within 3 days of the initiation of maximal supportive care is a DLT.
- e. Any \geq Grade 3 neurotoxicity (to include but not limited to limbic encephalitis, autonomic neuropathy, including peripheral neuromotor syndromes such as myasthenia gravis and Guillain-Barré) irrespective of duration is a DLT.

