- f. Any \geq Grade 3 cardiotoxicity (to include but not limited to arrhythmias, myocarditis with cardiomyopathy, ventricular dysfunction) irrespective of duration is a DLT.
- g. Any \geq Grade 3 ocular toxicity (including but not limited to iritis, uveitis, significant vision changes) irrespective of duration is a DLT.

Version Number: 1.8 Date: July 26, 2019

Proprietary of MD Anderson Cancer Center

- h. Any ≥ Grade 3 irAE, excluding colitis or pneumonitis or neurotoxicity or cardiotoxicity and ocular toxicity as mentioned above, that does not downgrade to Grade 2 within 3 days after onset of the event despite optimal medical management including systemic corticosteroids or does not downgrade to ≤ Grade 1 or baseline within 14 days.
- i. AST or ALT elevation $> 8 \times ULN$ or TBL $> 5 \times ULN$.
- j. Any \geq Grade 3 non-irAE, except for the exclusions listed below.
- k. Grade 3 or greater injection site reaction that is persistent beyond 5 days or does not downgrade to ≤ Grade 1 in 14 days.
- 1. Grade 3 or greater fever, not associated with above listed events (a to f), assessed by Principal Investigator as related to study treatment.
- m. Grade 3 or greater systemic symptoms, not associated with above listed events (a to e), assessed by Principal Investigator as related to study treatment.
- n. Any Grade 3 or greater anaphylaxis related to study treatment.
- o. Death that is at least possibly related to the study treatment.

The DLT definition excludes the following conditions:

- a. Grade 3 fatigue lasting ≤ 7 days.
- b. Grade 3 endocrine disorder (thyroid, pituitary, and/or adrenal insufficiency) that is managed with or without systemic corticosteroid therapy and/or hormone replacement therapy and the patient is asymptomatic.
- c. Grade 3 inflammatory reaction attributed to a local anti-tumor response (e.g., inflammatory reaction at sites of metastatic disease, lymph nodes, etc.).
- d. Concurrent vitiligo or alopecia of any AE grade.
- e. Grade 3 infusion-related reaction (first occurrence and in the absence of steroid prophylaxis) that resolves within 6 hours with appropriate clinical management.
- f. Grade 3 or 4 neutropenia that is not associated with fever or systemic infection that improves by at least one grade within 3 days. Grade 3 or Grade 4 febrile neutropenia will be a DLT regardless of duration or reversibility.
- g. Grade 3 or 4 lymphopenia.

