function tests [LFTs]) Infliximab should not be used for management of immune-related hepatitis	elevation (CTCAE version 4.03) Any grade Grade 1 (AST or ALT > upper limit of normal [ULN] to 3 times ULN and/or TBL > ULN to 1.5 times ULN)	No dose modification. If it worsens, treat as Grade 2 event.	 alkaline phosphatase (ALP), and total bilirubin (TBL) Evaluate for alternative etiologies (e.g., viral hepatitis, disease progression, concomitant medications). For Grade 1 AST or ALT and/or TBL elevation Continue LFT monitoring per protocol.
	Grade 2 (AST or ALT > 3 to 5 times ULN and/or TBL > 1.5-3.0 times ULN)	 Hold study drug/study regimen dose until Grade 2 resolution to ≤ Grade 1 If toxicity worsens then treat as Grade 3 or Grade 4 Study drug/study treatment can be resumed based upon treating physician's clinical judgment at the next scheduled dose once event stabilizes to Grade ≤ 1 or baseline and 5-7 days have passed after completion of steroid taper. 	 For Grade 2 AST or ALT and or TBL elevation: Regular and frequent checking of LFTs (e.g., every 1-2 days) until elevations of these are improving or resolved. If no resolution to ≤ Grade 1 in 1-2 days, discuss with Study Physician. If event is persistent (> 3-5 days) or worsens, promptly start prednisone 1-2 mg/kg/day or IV equivalent. If still no improvement within 3-5 days despite 1-2 mg/kg/day of prednisone or IV equivalent, consider additional work-up and prompt treatment with IV methylprednisolone 2-4 mg/kg/day started. If still no improvement within 3-5 days despite 2-4 mg/kg/day of IV methylprednisolone, promptly start immunosuppressives (mycophenolate mofetil)⁴. Discuss with Study Physician if mycophenolate mofetil is not available. Infliximab should NOT be used. Once improving, gradually taper steroids over ≥ 28 days and consider prophylactic antibiotics, antifungals and anti PCP treatment (please refer to current NCCN guidelines for treatment of cancer-related infections [Category 2B recommendation]).
	Grade 3 (AST or ALT > 5-20 times ULN and/or TBL > 3.0-10 times ULN	 For elevations in transaminases ≤ 8 × ULN, or elevations in bilirubin ≤ 5 × ULN Hold study drug/study regimen dose until resolution to ≤ Grade 1 or baseline 	 For Grade 3 or 4 AST or ALT and/or TBL elevation: Promptly initiate empiric IV methylprednisolone at 1 to 4 mg/kg/day or equivalent. If still no improvement within 3-5 days despite 1 to 4 mg/kg/day methylprednisolone IV or equivalent,

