⁴ ASCO Educational Book 2015 "Managing Immune Checkpoint Blocking Antibody Side Effects", by Michael Postow MD

Version Number: 1.8
Date: July 26, 2019

Proprietary of MD Anderson Cancer Center

Date: July 26, 2019		1 7	
	Grade 4 (AST or ALT > 20 times ULN and/or TBL > 10 times ULN)	 Resume study drug/study regimen administration at the next scheduled dose if elevations downgrade ≤ Grade 1 or baseline Permanently discontinue study drug/study regimen if the elevations do not downgrade to ≤ Grade 1 For elevations in transaminases > 8 × ULN or elevations in bilirubin > 5 × ULN, discontinue study drug/study regimen Permanently discontinue study drug/study regimen for any case meeting Hy's Law criteria (ALT > 3 × ULN + bilirubin > 2 × ULN without initial findings of cholestasis (i.e., elevated alkaline P04) and in the absence of any alternative cause⁵ Permanently discontinue study drug/study regimen. 	promptly start treatment with immunosuppressive therapy (mycophenolate mofetil). Discuss with Study Physician if mycophenolate is not available. Infliximab should NOT be used. - Hepatology consult, abdominal work-up, and imaging as appropriate. - Once improving, gradually taper steroids over ≥ 28 days and consider prophylactic antibiotics, antifungals and anti PCP treatment (please refer to current NCCN guidelines for treatment of cancer-related infections [Category 2B recommendation]).
Nephritis or renal dysfunction (elevated serum creatinine)	Grade of elevated serum creatinine (CTCAE version 4.03) Any grade Grade 1 [serum	No dose modification	 Consult with nephrologist. Monitor for signs and symptoms that may be related to changes in renal function (e.g., routine urinalysis, elevated serum blood urea nitrogen and creatinine, decreased creatinine clearance, electrolyte imbalance, decrease in urine output, proteinuria, etc). Subjects should be thoroughly evaluated to rule out any alternative etiology (e.g., disease progression, infections etc). Steroids should be considered in the absence of clear alternative etiology even for low grade events (Grade 2), in order to prevent potential progression to higher grade event. For Grade 1 elevated creatinine:
	creatinine > 1-1.5 × baseline; > ULN to 1.5 × ULN]	140 dose modification	 Monitor serum creatinine weekly and any accompanying symptom If creatinine returns to baseline, resume its regular monitoring per study protocol.

-

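### The Grade 3 hepatitis row of Table 7 has overlapping hold and discontinue triggers, which leaves resumption of durvalumab unsettled for a small group of patients

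*Combined protocol and SAP*

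**What the plan says.** Section 6.7.1 states that "there are certain circumstances in which durvalumab should be permanently discontinued" and refers to Appendix D for them. In Appendix D, Table 7, Grade 3 hepatitis is "AST or ALT > 5-20 times ULN and/or TBL > 3.0-10 times ULN", so the row covers isolated and joint elevations. The dose-modification cell has three parts:

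- **Hold.** "For elevations in transaminases ≤ 8 × ULN, or elevations in bilirubin ≤ 5 × ULN": hold until recovery, then "Resume study drug/study regimen administration at the next scheduled dose if elevations downgrade ≤ Grade 1 or baseline". If the values do not come down to Grade 1 or lower, discontinuation is permanent.
- **Discontinue.** "For elevations in transaminases > 8 × ULN or elevations in bilirubin > 5 × ULN, discontinue study drug/study regimen".
- **Hy's Law.** Permanent discontinuation for a case with "ALT > 3 × ULN + bilirubin > 2 × ULN without initial findings of cholestasis" and no alternative cause.

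Other sections also bear on these patients:

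- **6.7.2 item i with 3.4.** AST or ALT above 8 × ULN, or bilirubin above 5 × ULN, is a DLT, and a DLT ends study treatment. The evaluation period is "4 weeks after the first dose of durvalumab is administered for the initial six patients". Section 8.1.3 monitors DLT in all 34 subjects of a cohort.
- **7.6.4.** If the cause is confirmed and unrelated to study treatment, continuation is left to the investigator. If no cause is established, dosing is interrupted at once.
- **Appendix B.** AST or ALT at least 3 × ULN with bilirubin at least 2 × ULN is a potential Hy's Law case whatever the ALP, and it goes to review with the Study Physician.

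**The concern.** The hold and discontinue bullets read like two halves of one rule, split at 8 × ULN for transaminases and 5 × ULN for bilirubin. They are not two halves. The opposite of 'either value is above its cut-off' is 'neither value is above its cut-off', whereas the hold bullet says that one *or* the other is at or below its cut-off. A patient with one value above and the other raised but below satisfies both bullets. One allows durvalumab again after recovery and the other does not, and the row does not say which prevails.

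The stake is re-exposure to durvalumab after severe liver injury, or its refusal, with two investigators able to reach opposite answers from the same text. Sample size, error rates and efficacy analyses are not affected.

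**Working it through.** The plan gives no figure to reproduce, so the check is one of logic.

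**Inputs** (multiples of ULN; T is the higher transaminase, B is bilirubin), all from the Grade 3 row of Table 7:

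- Both values Grade 3, neither Grade 4: 5 < T ≤ 20 and 3 < B ≤ 10.
- Hold: T ≤ 8 or B ≤ 5.
- Discontinue: T > 8 or B > 5.
- Hy's Law laboratory values: ALT > 3 and B > 2.

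**Step 1: size of the overlap when both values are Grade 3.** The range is a rectangle of (20 − 5) × (10 − 3) = 105 units. The cut-offs divide it into four:

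| T | B | Units | Hold | Discontinue |
|---|---|---|---|---|
| 5 to 8 | 3 to 5 | 3 × 2 = 6 | yes | no |
| above 8 | 3 to 5 | 12 × 2 = 24 | yes | yes |
| 5 to 8 | above 5 | 3 × 5 = 15 | yes | yes |
| above 8 | above 5 | 12 × 5 = 60 | no | yes |

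The overlap is 24 + 15 = 39 of 105 (37%). Counted in steps of 0.1 × ULN, it is 120 × 20 + 30 × 50 = 3,900 of 150 × 70 = 10,500 value pairs, which is the same share. Two examples are T 10 with B 4, and T 6 with B 7.

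**Step 2: a second value that is raised but below Grade 3.** Take T from 1.1 to 20.0 and B from 1.1 to 10.0 in steps of 0.1, with at least one value Grade 3. That gives 190 × 90 − 40 × 20 = 16,300 pairs. The overlap is 120 × 40 + 70 × 50 = 8,300, so 8,300 − 3,900 = 4,400 pairs have a second value below Grade 3. These count only on a literal reading. Many readers would apply the discontinue bullet alone to ALT 10 × with bilirubin 1.5 × ULN.

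**Step 3: which overlap cases are settled elsewhere.**

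- *Hy's Law bullet.* Every both-Grade-3 pair has T > 5 and B > 3. If the raised transaminase is ALT, the laboratory values are met, and the row requires permanent discontinuation unless there is cholestasis or an alternative cause.
- *DLT stop.* A treatment-related case inside the window ends treatment. Whether 6.7.2 covers only the initial six patients or, following 8.1.3, everyone, the only stated window is 4 weeks. With dosing every 4 weeks and at most 13 doses (4.4.2), that is the first of up to 13 intervals.
- *7.6.4.* A confirmed unrelated cause goes to investigator judgment.
- *Appendix B.* All 3,900 pairs meet the potential Hy's Law values, subject to the rule that the transaminase rise must not follow the bilirubin rise. The case is reviewed, but no resumption rule is given.

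**Step 4: what is left, outside the DLT window.**

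- Cholestasis without a confirmed unrelated cause, for example ALT 10 ×, bilirubin 4 × ULN and raised ALP. The Hy's Law bullet in the row does not apply.
- AST-driven cases with ALT not above 3 × ULN, for example AST 10 ×, ALT 2.5 ×, bilirubin 4 × ULN. The row's Hy's Law wording names ALT only, although Appendix B counts AST or ALT.

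In both groups, if values return to Grade 1 or lower or to baseline, the text supports both resumption and discontinuation.

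**The case against.** The strongest reply is that the row already has a natural reading. The discontinue bullet is unconditional, so any value above either cut-off means stop. The same cut-offs define a DLT, and the 'or' in the hold bullet is there only so that isolated elevations are covered. Most clinicians would probably choose the stricter bullet. That makes harm unlikely, but it supplies a precedence the text does not state. The bullet also says only 'discontinue', while the bullets next to it say that discontinuation is permanent, which weakens the inference that it overrides an express permission to resume.

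The second reply is that Appendix B closes the gap. If the cause cannot be assessed within 3 weeks, no alternative explanation is assumed until an informed decision can be made. This points towards the Hy's Law bullet and largely disposes of cases whose only open question is a suspected but unconfirmed cause. But that default is written for SAE reporting, and it does not lift the cholestasis condition in Table 7. Appendix B's definition also gives a fair argument that AST-driven cases should count as Hy's Law, but the row says otherwise.

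It is also true that Table 7 is recommended guidance and that 3.5 has discontinuations discussed with the medical monitor. Both soften the problem without saying which bullet governs.

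A reader might infer something stronger: that resumption is unsettled for every patient with two raised liver values, or that patients keep being dosed through severe hepatitis. The documents support neither. The provisions in step 3 settle most cases, and both bullets, with 7.6.4 where no cause is established, stop dosing at onset.

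**Conclusion.** The row is wrong as written, and the consequence is minor. The hold and discontinue triggers overlap whenever both liver values are raised and exactly one exceeds its cut-off. That is 37% of the both-Grade-3 value range. This percentage describes combinations of values and must not be read as a frequency: the documents do not say how many patients show such patterns, and the number is probably small.

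After the other provisions are applied, the open cases are a small residue outside the DLT window, mainly the two groups in step 4. For them the only unsettled question is resumption after recovery. The conclusion assumes that the row's Hy's Law wording is taken as printed (ALT only, no initial cholestasis) and that the DLT rule does not extend beyond its stated 4 weeks. If Appendix B's AST-or-ALT definition were taken to govern Table 7, AST-driven cases with no other explanation would be settled as well, leaving mainly the cholestatic ones.

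**What to change.** Reword the hold bullet to: *For Grade 3 elevations where neither transaminases exceed 8 × ULN nor bilirubin exceeds 5 × ULN*. Leave the discontinue bullet as it is. 'Neither T > 8 nor B > 5' is the exact negation of 'T > 8 or B > 5', so every Grade 3 case falls under exactly one bullet. ALT 10 × with bilirubin 4 × ULN leads to discontinuation, in line with 6.7.2 item i. Isolated elevations stay covered: ALT 6 × with normal bilirubin is held, and ALT 10 × with normal bilirubin is discontinued.

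Simply changing 'or' to 'and' is less safe, because it can be read as requiring both values to be elevated, which would leave isolated elevations without a hold instruction.

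The cost is a few words at the next amendment, with no added data or patients. The downside is that a few patients who might have been rechallenged after recovery would stop durvalumab.
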